8.1. Serious Adverse Events

8.1.1. Definition of Serious Adverse Event (SAE)

An SAE is any event that meets any of the following criteria at any dose:

- Death
- Life-threatening
- Inpatient hospitalization or prolongation of existing hospitalization
- Persistent or significant disability/incapacity
- Congenital anomaly/birth defect in the offspring of a subject who received rimegepant
- Other Important Medical Events: that may not result in death, be life-threatening, or require hospitalization, may be considered an SAE when, based upon appropriate medical judgment, they may jeopardize the subject and may require medical or surgical intervention to prevent one of the outcomes listed in this definition. Examples of such events are (but not limited to):
 - Intensive treatment in an emergency room or at home for allergic bronchospasm
 - Blood dyscrasias or convulsions that do not result in inpatient hospitalization
 - Development of drug dependency or drug abuse

- Potential drug induced liver injury (see [Section 8.4](#))
- Abuse or Overdose of medication
 - i. Potential study drug abuse (including cases of excessive non-compliance with study drug dosing instructions or subjects who discontinue treatment without returning study drug) is to be documented in the source record and reported as an AE or SAE, as appropriate. Investigators must monitor subjects for possible cases of abuse of study drug (subjects taking study drug for non-therapeutic purposes, e.g., for psychoactive effects such as high or euphoria). Investigators are to obtain more information and explanation from subjects when there are study drug accountability discrepancies
 - ii. Potential study drug overdose is defined in [Section 8.3](#)

In general, hospitalization signifies that the subject has been detained (usually involving at least an overnight stay) at the hospital or emergency ward for observation and/or treatment that would not have been appropriate in the physician's office or outpatient setting. When in doubt as to whether 'hospitalization' occurred or was necessary, the AE is to be considered serious.

The following hospitalizations are not considered SAEs in Pfizer clinical studies (but may be considered non-serious AEs):

- A visit to the emergency room or other hospital department <24 hours that does not result in an admission (unless considered “important medical event” or event that is life threatening);
- Elective surgery planned prior to signing consent;
- Admissions as per protocol for a planned medical/surgical procedure;
- Routine health assessment requiring admission (i.e., routine colonoscopy);
- Admission encountered for another life circumstance that carries no bearing on health and requires no medical intervention (i.e., lack of housing, care-giver respite, family circumstances).

Disability/incapacitating: An AE is incapacitating or disabling if the experience results in a substantial and/or permanent disruption of the subject's ability to carry out normal life functions.

8.1.2. Collection and Reporting Serious Adverse Events

Following the subject's written consent to participate in the study, all SAEs, whether related or not related to study drug, must be collected, including those thought to be associated with protocol-specific procedures. All SAEs must be collected from signing of consent through

the Follow-up Week 2 Visit. Unresolved SAEs at the time of the Follow-up Week 2 Visit should be monitored until resolution of the acute aspects of the safety event, per the opinion of the Investigator. The Investigator should report any SAE occurring beyond the Follow-up Week 2 Visit when the event is believed to be related to study drug or other protocol-specific procedures.

All SAEs must be followed to resolution or stabilization.

An SAE report must be completed for any event where doubt exists regarding its status of seriousness.

If the Investigator believes that an SAE is not related to the study drug but is potentially related to the conditions of the study (such as a withdrawal of previous therapy or a complication related to study procedure), the relationship must be specified in the narrative section of the SAE Report Form.

SAEs, whether related or not related to study drug, overdose (see [Section 8.3](#)), potential drug induced liver injury (see [Section 8.4](#)) and pregnancies (see [Section 8.5.1](#)) must be reported within 24 hours of the Investigator becoming aware of the event. The Investigator is responsible for submitting all applicable events to the Independent Review Board (IRB) as per the IRB's reporting requirements. Additionally, the Investigator, or designated staff, is responsible for entering the SAE information into the Case Report Form (CRF) and/or system (i.e., event term, start/stop dates, causality, and severity).

The Investigator is responsible for reporting all SAEs and all Other Important Medical Events to Pfizer Drug Safety Unit (DSU) within 24 hours of learning of the event. Pfizer DSU will then immediately notify the Medical Monitor of the event. The Investigator is responsible for submitting all applicable events to the Independent Review Board (IRB)/ EC as per the IRB's reporting requirements. Additionally, the Investigator, or designated staff, is responsible for entering the SAE information in the Electronic Data Capture (EDC) system (i.e., event term, start/stop dates, causality, severity).

Any serious adverse event must be reported immediately or no later than 24 hours after awareness of the event to Pfizer DSU either via the Pfizer SAE Submission Assistant (PSSA) tool or as a written description using the Pfizer CT SAE report form, that must be sent by facsimile (fax) to your country's Pfizer DSU. The CT SAE Report Form should only be used as a backup in the event PSSA is not operational.

If only limited information is initially available, follow-up reports are required. If an ongoing SAE changes in its intensity or relationship to study drug or if new information becomes available, a follow-up SAE report must be sent within 24 hours of the Investigator becoming aware of the updated information using the same procedure used for the transmission of the initial SAE and the same event term is to be used.

The minimum information required for an initial SAE report is:

- Sender of report (Site number, Investigator name)
- Subject identification (subject number)
- Protocol number
- SAE term (if an SAE is being reported)

The Sponsor or specified designee/authorized representative will report suspected unexpected serious adverse reactions (SUSARs) in an expedited manner (without delay) to the Regulatory Authorities and Ethics Committees concerned, in accordance with Food and Drug Administration Code of Federal Regulations (CFR) 21 CFR Parts 312 and 320, Clinical Trials Regulation EU No 536/2014 and the Detailed Guidance on collection, verification and presentation of adverse reaction reports arising from clinical trials on IPs for human use (ENTR/CT3) and also in accordance with country-specific requirements.

The Sponsor or specified designee/authorized representative shall notify the Investigator of the following information:

- Any AE that is both serious and unexpected and is suspected of being related to the use of the IP in this study or in other studies (i.e., SUSAR).
- Where required by local legislation, the Investigator shall notify his/her IRB/EC promptly of these new serious and unexpected AE(s) or significant risks to subjects.

8.2. Non-serious Adverse Events

A *non-serious adverse event* is an AE not classified as serious.

8.2.1. Collection and Reporting of Non-serious Adverse Events

The collection of non-serious AE information is to begin from signing the ICF through the Follow-up Week 2 Visit.

Non-serious adverse events are to be followed until conclusion or stabilization or reported as SAEs if they become serious. Follow-up is also required for non-serious AEs that cause interruption or discontinuation of study drug or those that are present at the end of study treatment.

8.2.2. Laboratory Test Abnormalities

The following laboratory test abnormalities are to be captured on the non-serious AE CRF page or SAE Report Form (paper or electronic) as appropriate:

- a. Any laboratory test result that is clinically significant or meets the definition of an SAE;

- b. Any laboratory abnormality that required the subject to have the study drug discontinued or interrupted;
- c. Any laboratory abnormality that required the subject to receive specific corrective therapy.

8.3. Overdose

An overdose is defined as the accidental or intentional administration of any dose of a product that is considered both **excessive AND medically important**.

There is limited clinical experience with overdose of rimegepant. Treatment of overdose with rimegepant should consist of general supportive measures. There is no known specific antidote for overdose with rimegepant.

Overdose is reportable to Pfizer Safety only when associated with an SAE.

- Cases of study drug non-adherence, including subjects who discontinue treatment without returning study drug, are to be reported as protocol deviations.
- Cases of excess dosing (e.g., taking >1 tablet of study medication in a single day) are to be reported as protocol deviations. In the event that an occurrence(s) of excess dosing is believed, in the opinion of the Principal Investigator, to have possibly caused or exacerbated a clinically-significant adverse outcome or serious adverse outcome, such event(s) are to be reported as an AE or SAE, respectively, of “Overdose”.
- Asymptomatic dosing errors (e.g., accidentally taking >1 tablet of study drug in one calendar day) need only be reported as deviations.

8.4. Potential Drug Induced Liver Injury (DILI)

Humans exposed to a drug who show no sign of liver injury (as determined by elevations in transaminases) are termed “tolerators,” while those who show transient liver injury but adapt are termed “adaptors.” In some subjects, transaminase elevations are a harbinger of a more serious potential outcome. These subjects fail to adapt and therefore are “susceptible” to progressive and serious liver injury, commonly referred to as DILI. Subjects who experience a transaminase elevation above $3 \times \text{ULN}$ should be monitored more frequently to determine if they are “adaptors” or are “susceptible.”

In the majority of DILI cases, elevations in AST and/or ALT precede T bili elevations ($>2 \times \text{ULN}$) by several days or weeks. The increase in T bili typically occurs while AST/ALT is/are still elevated above $3 \times \text{ULN}$ (ie, AST/ALT and T bili values will be elevated within the same laboratory sample). In rare instances, by the time T bili elevations are detected, AST/ALT values might have decreased. This occurrence is still regarded as a potential DILI. Therefore, abnormal elevations in either AST OR ALT in addition to T bili that meet the criteria outlined below are considered potential DILI (assessed per Hy’s law criteria) cases

and should always be considered important medical events, even before all other possible causes of liver injury have been excluded.

The threshold of laboratory abnormalities for a potential DILI case depends on the subject's individual baseline values and underlying conditions. Subjects who present with the following laboratory abnormalities should be evaluated further as potential DILI (Hy's law) cases to definitively determine the etiology of the abnormal laboratory values:

- Subjects with AST/ALT and T bili baseline values within the normal range who subsequently present with AST OR ALT values $\geq 3 \times \text{ULN}$ AND a T bili value $\geq 2 \times \text{ULN}$ with no evidence of hemolysis and an alkaline phosphatase value $< 2 \times \text{ULN}$ or not available.
- For subjects with baseline AST **OR** ALT **OR** T bili values above the ULN, the following threshold values are used in the definition mentioned above, as needed, depending on which values are above the ULN at baseline:
 - Preexisting AST or ALT baseline values above the normal range: AST or ALT values ≥ 2 times the baseline values AND $\geq 3 \times \text{ULN}$; or $\geq 8 \times \text{ULN}$ (whichever is smaller).
 - Preexisting values of T bili above the normal range: T bili level increased from baseline value by an amount of $\geq 1 \times \text{ULN}$ **or** if the value reaches $\geq 3 \times \text{ULN}$ (whichever is smaller).

Rises in AST/ALT and T bili separated by more than a few weeks should be assessed individually based on clinical judgment; any case where uncertainty remains as to whether it represents a potential Hy's law case should be reviewed with the sponsor.

The subject should return to the investigator site and be evaluated as soon as possible, preferably within 48 hours from awareness of the abnormal results. This evaluation should include laboratory tests, detailed history, and physical assessment.

If any potential DILI is identified and meets the criteria above, the Sponsor Medical Monitor (or designee) must be immediately contacted for further instruction on whether the subject must discontinue from the trial and appropriate follow-up requirements.

All cases demonstrated on repeat testing as meeting the laboratory criteria of AST/ALT and T bili elevation defined above should be considered potential DILI (Hy's law) cases if no other reason for the LFT abnormalities has yet been found. **Such potential DILI (Hy's law) cases are to be reported as SAEs, irrespective of availability of all the results of the investigations performed to determine etiology of the LFT abnormalities.**

A potential DILI (Hy's law) case becomes a confirmed case only after all results of reasonable investigations have been received and have excluded an alternative etiology.

8.5. Environmental Exposure, Exposure During Pregnancy or Breastfeeding, and Occupational Exposure

Environmental exposure occurs when a person not enrolled in the study as a subject receives unplanned direct contact with or exposure to the study intervention. Such exposure may or may not lead to the occurrence of an AE or SAE. Persons at risk for environmental exposure include healthcare providers, family members, and others who may be exposed. An environmental exposure may include EDP, EDB, and occupational exposure.

Any such exposures to the study intervention under study are reportable to Pfizer Safety within 24 hours of investigator awareness.

8.5.1. Exposure During Pregnancy

If, following the Baseline Visit it is subsequently discovered that a study subject is pregnant or may have been pregnant at the time of the investigational product exposure, including during at least 6 half-lives after the product administration, the investigational product will be permanently discontinued in an appropriate manner (i.e., dose tapering if necessary for subject safety). Protocol-required procedures for the study discontinued and the follow-up must be performed on the subject unless contraindicated by the pregnancy (i.e., x-ray studies). Other appropriate pregnancy follow-up procedures should be considered if indicated. The investigator must immediately notify the Pfizer (or designee) Medical Monitor and report the event by either using the PSSA tool and by completing an Exposure During Pregnancy (EDP) Supplemental Form following the SAE reporting procedures as described in [Section 8.1.2](#).

Follow-up information regarding the course of the pregnancy, including perinatal and neonatal outcome and, where applicable offspring information must be reported on an EDP Supplemental Form.

Any pregnancy that occurs in a female partner of a male study should be reported to Pfizer DSU. Information on this pregnancy will be collected on an EDP Supplemental Form, as appropriate.

An EDP occurs if:

- A female subject is found to be pregnant while receiving or after discontinuing study intervention.
- A male subject who is receiving or has discontinued study intervention inseminates a female partner.

- A female subject is found to be pregnant while being exposed or having been exposed to study intervention because of environmental exposure. Below are examples of environmental EDP:
 - A female family member or healthcare provider reports that she is pregnant after having been exposed to the study intervention by ingestion or skin contact.
 - A male family member or healthcare provider who has been exposed to the study intervention by ingestion or skin contact then inseminates his female partner prior to or around the time of conception.

The investigator must report EDP to Pfizer Safety within 24 hours of the investigator's awareness, irrespective of whether an SAE has occurred. The initial information submitted should include the anticipated date of delivery (see below for information related to termination of pregnancy).

- If EDP occurs in a subject/subject's partner, the investigator must report this information to Pfizer Safety using the CT SAE Report Form and EDP supplemental form or via PSSA, regardless of whether an SAE has occurred. Details of the pregnancy will be collected after the start of study intervention and until 66 hours after the last dose.
- If EDP occurs in the setting of environmental exposure, the investigator must report information to Pfizer Safety using the CT SAE Report Form and EDP supplemental form or via PSSA. Since the exposure information does not pertain to the subject enrolled in the study, the information is not recorded on a CRF; however, a copy of the completed report is maintained in the investigator site file.

Follow up is conducted to obtain general information on the pregnancy and its outcome for all EDP reports with an unknown outcome. The investigator will follow the pregnancy until completion (or until pregnancy termination) and notify Pfizer Safety of the outcome as a follow up to the initial report. In the case of a live birth, the structural integrity of the neonate can be assessed at the time of birth. In the event of a termination, the reason(s) for termination should be specified and, if clinically possible, the structural integrity of the terminated fetus should be assessed by gross visual inspection (unless pre-procedure test findings are conclusive for a congenital anomaly and the findings are reported).

Abnormal pregnancy outcomes are considered SAEs. If the outcome of the pregnancy meets the criteria for an SAE (ie, ectopic pregnancy, spontaneous abortion, intrauterine fetal demise, neonatal death, or congenital anomaly [in a live born baby, a terminated fetus, an intrauterine fetal demise, or a neonatal death]), the investigator should follow the procedures for reporting SAEs. Additional information about pregnancy outcomes that are reported to Pfizer Safety as SAEs follows:

- Spontaneous abortion including miscarriage and missed abortion should be reported as an SAE;
- Neonatal deaths that occur within 1 month of birth should be reported, without regard to causality, as SAEs. In addition, infant deaths after 1 month should be reported as SAEs when the investigator assesses the infant death as related or possibly related to exposure to the study intervention.

Additional information regarding the EDP may be requested by the sponsor. Further followup of birth outcomes will be handled on a case by case basis (eg, follow-up on preterm infants to identify developmental delays). In the case of paternal exposure, the investigator will provide the subject with the Pregnant Partner Release of Information Form to deliver to his partner. The investigator must document in the source documents that the subject was given the Pregnant Partner Release of Information Form to provide to his partner.

8.5.2. Exposure During Breastfeeding

An EDB occurs if:

- A female subject is found to be breastfeeding while receiving or after discontinuing study intervention.
- A female non subject is found to be breastfeeding while being exposed or having been exposed to study intervention (ie, environmental exposure). An example of environmental EDB is a female family member or healthcare provider who reports that she is breastfeeding after having been exposed to the study intervention by ingestion.

The investigator must report EDB to Pfizer Safety within 24 hours of the investigator's awareness, irrespective of whether an SAE has occurred. The information must be reported using the CT SAE Report Form or PSSA. When EDB occurs in the setting of environmental exposure, the exposure information does not pertain to the subject enrolled in the study, so the information is not recorded on a CRF. However, a copy of the completed report is maintained in the investigator site file.

An EDB report is not created when a Pfizer drug specifically approved for use in breastfeeding women (eg, vitamins) is administered in accordance with authorized use. However, if the infant experiences an SAE associated with such a drug, the SAE is reported together with the EDB.

8.5.3. Occupational Exposure

The investigator must report any instance of occupational exposure to Pfizer Safety within 24 hours of the investigator's awareness using the CT SAE Report Form or PSSA, regardless of whether there is an associated SAE. Since the information about the occupational exposure does not pertain to a subject enrolled in the study, the information is not recorded on a CRF; however, a copy of the completed report is maintained in the investigator site file.

8.5.4. Lack of Efficacy

The investigator must report signs, symptoms, and/or clinical sequelae resulting from lack of efficacy. Lack of efficacy or failure of expected pharmacological action is reportable to Pfizer Safety only if associated with an SAE.

8.5.5. Medication Errors

Medication errors may result from the administration or consumption of the study intervention by the wrong subject, or at the wrong time, or at the wrong dosage strength.

Medication errors are recorded and reported as follows:

Recorded on the Adverse Event Page of the CRF	Reported on the PSSA* to Pfizer Safety Within 24 Hours of Awareness
All medication errors (regardless of whether associated with an AE). Any AE or SAE associated with the medication error	Only if associated with an SAE

*The CT SAE Report Form should only be used as a backup in the event PSSA is not operational

Medication errors include:

- Medication errors involving subject exposure to the study drug;
- Potential medication errors or uses outside of what is foreseen in the protocol that do or do not involve the study subject.
- The administration of expired study drug;
- The administration of an incorrect study drug;
- The administration of an incorrect dosage:
 - Subjects taking > 2 tablets in one calendar day

- The administration of study drug that has undergone temperature excursion from the specified storage range, unless it is determined by the sponsor that the study drug under question is acceptable for use.

If applicable, any associated serious and nonserious AE(s) are recorded on the AE page of the CRF.

In the event of a medication dosing error, the sponsor should be notified within 24 hours. Medication errors should be reported to Pfizer Safety within 24 hours via PSSA **only when associated with an SAE**.

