³ During the OLE Phase, WOCBP must complete a pregnancy test at the Week 2, Week 4, Week 8, Week 12/EOT, and Follow-up Week 2 Visits. If a WOCBP suspects that she might be pregnant she must not take any further doses of study drug and immediately contact the study doctor

	Open-label Extension Phase					Follow-up Phase	
Procedure	Eligibility Confirmation Phone Visit ¹	Week 2 Visit (OLE Day 15 +/- 2 days)	Week 4 Visit (OLE Day 29 +/- 2 days)	Week 8 Visit (OLE Day 57 +/- 2 days)	Week 12 Visit (OLE Day 85 +/- 2 days) or EOT for early discontinuation	Follow-up Week 2 Visit (+/- 2days)	NOTES
AE, SAE, and Concomitant Procedure assessment		X	X	X	X	X	AEs and SAEs are collected through the Follow-up Week 2 Visit
Clinical Drug Supplies /Study Supplies							
Dispense study drug ⁴		X	X	X			
Administer study drug		X	X	X			Subjects cannot take more than 1 ODT of study drug (rimegepant) per day, and no more than 18 tablets of rimegepant per 28 days. Study drug is NOT to be used for rescue.
Return used and unused study drug to site for compliance check		X	X	X	X		
eDiary returned / reviewed for completeness ⁵		X	X	X	X		Subject will return eDiary. Site staff to review and confirm all data points are transferred, PRIOR to the subject leaving the study center.

⁴ At the DBT Phase EOT Visit, subjects will be administered 2 wallet cards containing 8 ODTs. Subjects are to be instructed to complete a full wallet, as directed, before taking study drug from a new one. Day 1 of the OLE Phase = DBT EOT Visit.

⁵ eDiary will be used to record the occurrence of migraine attacks and headaches during the OLE Phase

	Open-label Extension Phase					Follow-up Phase	
Procedure	Eligibility Confirmation Phone Visit ¹	Week 2 Visit (OLE Day 15 +/- 2 days)	Week 4 Visit (OLE Day 29 +/- 2 days)	Week 8 Visit (OLE Day 57 +/- 2 days)	Week 12 Visit (OLE Day 85 +2 days) or EOT for early discontinuation	Follow-up Week 2 Visit (+/- 2days)	NOTES
Other Assessments							
Migraine-Specific Quality-of-Life Questionnaire (MSQ) v 2.1					X		Paper assessment.
Migraine Interictal Burden Scale (MIBS)			X	X	X		Paper assessment. Recall for this scale is every 4 weeks.
Migraine Quality of Life Questionnaire (MQoL)		X			X		Scale will populate on the eDiary 24 hours after each qualifying migraine attack until 5 are completed.
Columbia-Suicide Severity Rating Scale (C-SSRS)			X		X		Paper assessment. Since the last assessment will be used for all OL timepoints.

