7.1.7. Selection and Timing of Dose and Administration

Study drug will be assigned via the RTSM system; the system will assign specific kit numbers for all blinded study drug to be dispensed to the subject. Once a kit has been assigned it cannot be dispensed to another study subject. Sites will be responsible for recording the kit numbers dispensed to the subject on the Drug Accountability Form provided in the Regulatory Binder, as well as ensure appropriate documentation of dispensation in the subject's medical record.

For the DBT Phase, rimegepant 75 mg ODT or placebo will be assigned to subjects at the Baseline (Randomization) Visit via the RTSM system. Subjects will be instructed to administer 1 ODT when they have a migraine that is moderate or severe in headache pain intensity.

For the OLE Phase, rimegepant 75 mg ODT will be dispensed at study dispensation visits. Subjects must completely finish study drug wallets before starting new wallets.

There are no dose adjustments in this study.

Subjects **must** be instructed that they CANNOT take more than 1 tablet of study drug daily during the study and no more than 18 tablets of rimegepant per month (28 days).

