- Total OL rimegepant exposure (patient-years), derived by summing (OL rimegepant end date – OL rimegepant start date + 1)/365.25 across all subjects.

See Section 7.4.1 for tablet counts.

Tables of OL rimegepant exposure are also provided by subgroup level and overall for all high-level safety subgroups of interest described in Section 4.3.2.

6.2.6.2 *Measurements of Treatment Compliance*

The by-subject listing of treatment compliance is provided for the safety analysis set, and displays results for DB and OL rimegepant treatment compliance parameters in separate columns as flags (“Y” or missing).

DB Treatment Compliance

The frequency table of DB study drug treatment compliance is provided by treatment group for the DBT safety analysis set, and displays the following categories:

- DB study drug taken but not randomized. Defined as nonmissing DB study drug date and missing RTSM randomization date.
- DB study drug taken without having a qualifying migraine attack. Defined as nonmissing DB study drug date and no qualifying migraine attack at the time of DB study drug dosing (see Section 9.3.1).
- DB study drug actually received different from randomized treatment assignment (i.e., as-treated treatment group not equal to as-randomized treatment group). Defined as either of the following using the Drug Accountability CRF:
 - Randomized to rimegepant but the first wallet dispensed is DB placebo
 - Randomized to placebo but the first wallet dispensed is DB rimegepant.

Results for all categories are displayed, even those with 0 counts.

OL Rimegepant Treatment Compliance

The frequency table of treatment compliance is provided by treatment group for the OL rimegepant safety analysis set, and displays the following categories:

- >1 OL rimegepant tablet taken on any 1 day
- OL rimegepant taken before OLE Phase eligibility contact. Defined as OL rimegepant start date before the contact date from the OLE Phase Eligibility CRF.

- OL rimegepant taken without having a qualifying migraine attack. Defined as nonmissing OL rimegepant date and no qualifying migraine attack at the time of OL rimegepant dosing (see Section 9.3.1)
- Time on OL rimegepant ≥ 14 weeks (see Section 6.2.6.1)
- OL rimegepant taken but DB study drug never taken. Defined as missing DB study drug date/time.

Results for all categories are displayed, even those with 0 counts.

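### Protocol 8.5.5 sets its only numeric example of an incorrect dosage above 2 tablets a day, while 8.3 and the SAP act above 1, and the two protocol sections give different recording routes for asymptomatic excess dosing

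*Protocol*

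**What the plan says.** **Daily limit.** Protocol 7.1.7 says that subjects "CANNOT take more than 1 tablet of study drug daily during the study". The note in Table 2 (protocol 4.3) agrees: "Subjects cannot take more than 1 ODT of study drug (rimegepant) per day".

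**Protocol 8.3 (Overdose).** The threshold is more than 1 tablet: "Cases of excess dosing (e.g., taking >1 tablet of study medication in a single day) are to be reported as protocol deviations". If the investigator thinks the excess may have caused or worsened a clinically significant or serious outcome, it becomes an AE or SAE of overdose. Without symptoms the rule is lighter: "Asymptomatic dosing errors (e.g., accidentally taking >1 tablet of study drug in one calendar day) need only be reported as deviations".

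**Protocol 8.5.5 (Medication Errors).** Under incorrect dosage the only entry is "Subjects taking > 2 tablets in one calendar day". The same list has a general bullet for potential errors or uses that the protocol does not provide for, with no tablet number. All medication errors go on the AE page of the CRF, with or without an AE. The section adds: "In the event of a medication dosing error, the sponsor should be notified within 24 hours". Reporting to the safety unit is required only with an SAE.

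**SAP.** Sections 6.2.6.2 (treatment compliance) and 9.1 (relevant protocol deviations) both use the category ">1 OL rimegepant tablet taken on any 1 day".

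**The concern.** A site that learns of a 2-tablet day in the open-label extension has two operative safety sections to consult, and they do not use the same number. It also has two instructions on what to do when nothing clinical follows: file a deviation and stop, or make an AE-page entry and tell the sponsor within 24 hours. Protocol section 3 and SAP 3.2 take AE data from the AE and SAE CRF pages, so the number of AE-page entries for excess dosing could reflect which section a site read rather than what subjects did. The population includes subjects with a history of cardiovascular disease (a stratum capped at 15%), so uniform records of excess dosing are worth having.

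**Working it through.** No sample size, power or alpha is involved, and the plan states no figure to reproduce. The check classifies a day with 1, 2 or 3 tablets under each passage.

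| Tablets in one day | Limit in 7.1.7 and Table 2 | Protocol 8.3 | SAP 6.2.6.2 and 9.1 (open-label drug) | Numeric entry in 8.5.5 | General bullet in 8.5.5 |
|---|---|---|---|---|---|
| 1 | within limit | no excess | not counted | not met (1 is not above 2) | does not apply on tablet count |
| 2 | exceeded | excess dosing; deviation | counted | not met (2 is not above 2) | could apply |
| 3 | exceeded | excess dosing; deviation | counted | met (3 is above 2) | could apply |

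The passages agree at 1 tablet. At 2 tablets the numeric entry in 8.5.5 departs from all the others, and from the general bullet in its own list. At 3 tablets all the thresholds are passed.

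Next, the recording route when there are no symptoms:

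| Tablets in one day | Route under 8.3 | Route under 8.5.5 |
|---|---|---|
| 2 | deviation report is enough | none if the numeric entry governs; AE page plus 24-hour sponsor notice if the general bullet governs |
| 3 or more | deviation report is enough | AE page plus 24-hour sponsor notice |

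The second row shows that the route conflict does not depend on the number. If the two sections shared a threshold, an asymptomatic excess would still be a deviation only in 8.3 and an AE-page entry in 8.5.5.

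**Where it can arise.** Protocol 4.1 and 4.3.2 dispense a single tablet in the double-blind phase, so days with 2 or more tablets belong essentially to the open-label extension, where subjects hold wallets of 8 tablets (protocol 7.1.4).

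**What the SAP relies on.** Tablet counts come from eDiary dosing records and manual data-correction forms, one tablet per record (SAP 7.4.1.1 and 7.4.1.2), not from the 8.5.5 classification. The AE outputs listed in SAP 6.4.1.2 to 6.4.1.6 include no medication-error category.

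**The case against.** **The dosing limit is consistent.** Every dosing passage gives 1 tablet a day. A reader might infer that 8.5.5 permits a second tablet. It does not: its line is an example in a recording section. This objection stands.

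**A 2-tablet day need not be lost under 8.5.5.** Its list is introduced as inclusive rather than complete, and the general bullet can reach any dose above the limit. A reader might infer that 8.5.5 excludes 2-tablet days outright; the text does not go that far. This stands, but it leaves the section with a specific entry that implies exclusion and a general one that implies inclusion.

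**The analyses do not depend on it.** The SAP counts days above 1 tablet from dosing records, protocol 7.3 has sites check returned drug at each open-label visit, and clinical AEs are collected however the dose is classified. A reader might infer that excess-dosing counts or AE ascertainment will be incomplete. The documents do not support that. Whether an AE-page entry with no clinical event would enter an AE table cannot be judged, because the Core SAP is not supplied.

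**The sections could be tiers:** 2 tablets a deviation, 3 or more also a medication error. The protocol states no tiers. Section 8.3 already calls more than 1 tablet a dosing error, and 8.5.5 attaches the 24-hour notice to a dosing error without repeating its number. Tiers would also leave the 3-tablet conflict in place.

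**Section 8.3 may mean safety reporting only**, leaving AE-page recording to 8.5.5. That is possible, but the preceding bullet in 8.3 uses the same verb for reporting an AE or SAE, so a site can fairly read deviation-only as meaning no AE entry.

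**Conclusion.** The inconsistency is real and lies in current operative text. It has two parts: a numeric example in 8.5.5 that does not match the threshold in 8.3 and the SAP, with an ambiguity inside 8.5.5 for exactly 2 tablets; and a separate conflict of recording route for any asymptomatic excess that counts as a medication error, including 3 or more tablets.

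Its reach is narrow. It affects the consistency of AE-page entries and of 24-hour sponsor notices, essentially in the open-label extension. The SAP's compliance and deviation counts, the collection of actual AEs, the randomized comparison and the sample size are untouched. The documents do not say how many such days to expect; SAP 7.1 describes several records on the same date as rare.

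The conclusion assumes that sites work from the protocol text as written, with no separate instruction that settles the matter.

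**What to change.** Reconcile protocol 8.3 and 8.5.5 with each other and with the limit in 7.1.7 and Table 2, so that one threshold and one recording route apply to exceeding the daily limit. The wording should say whether an asymptomatic excess goes on the AE page, is filed as a deviation, or both, and whether the 24-hour sponsor notice applies. It should also remove the tension between the numeric entry and the general bullet in 8.5.5. Changing the tablet number alone would leave the route conflict. Then confirm that SAP 6.2.6.2 and 9.1, which already agree with 8.3, remain consistent with the result. Which threshold and route to adopt is for the sponsor to decide.

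The cost is a clarification letter or amendment wording. No analysis, sample size or data-collection form needs to change on the evidence in the documents.
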